Hypotheses #1 and #2. The change in the KCCQ Clinical Summary score from baseline to the end of the 12 weeks of treatment will be computed for each patient as KCCQ score at 12 weeks minus KCCQ score at baseline. A two-tailed independent samples t-test will test the null hypothesis of no difference in mean change between patients on ubiquinol and patients on placebo. Similar tests will be used to compare D-ribose with placebo, ubiquinol + D-ribose with placebo, and ubiquinol versus ubiquinol + D-ribose. Next, we state and justify the assumptions underlying our proposed sample size. Soto et al. (2004) conducted a study of 1516 patients and found that a 10-point decline in KCCQ scores had an important prognostic significance, in that patients whose KCCQ Clinical Summary scores declined by ≥ 10 points had a 107% increased risk of dying or being hospitalized during the next 12 weeks (event rate = 11.4% vs. 5.5%, $p < 0.001$).⁸⁵ Thus, we believe that an increase of at least 10 points with use of ubiquinol will be clinically important. In addition, our pilot study with ten subjects also found that, after 12 weeks of treatment, all subjects with ubiquinol or ubiquinol + D-ribose had an increase in the KCCQ Clinical Summary score of at least 10 points, which is consistent with the study findings of Soto et al. (2004). The combined estimated standard deviation for the increase was 12.3 points.

This implies that Cohen effect sizes of at least 0.81 ($= 10/12.3$) are clinically important. Therefore, a sample size of 62 subjects per group will provide at least 98% power to detect this or larger effect sizes at a nominal significance level of 0.05 (with Bonferroni correction for four comparisons).

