Hypothesis #4. A two-tailed independent samples t-test will be used to test the null hypothesis that the mean change in the 6MWT from baseline to the end of 12 weeks in patients taking ubiquinol is different from the mean change for placebo. Comparisons of D-ribose versus placebo, of ubiquinol + D-ribose versus placebo, and of ubiquinol versus ubiquinol + D-ribose will likewise be made. Our proposed sample sizes (62 per group) will allow detecting Cohen effect sizes on the 6MWT of at least 0.7 with at least 90% power at a nominal 0.05 level of significance with Bonferroni correction for four comparisons. Published data⁸⁶ suggest the possibility of a much larger effect size of ubiquinol on a 6-minute walk (3.9), giving us confidence in our design for at least the ubiquinol vs. placebo comparison.

Hypothesis #5. Our pilot data suggested that ubiquinol has a large effect size on BNP (-1.5 ; Table 2). Thus, two-tailed independent samples t-tests comparing changes in BNP from baseline to the end of 12 weeks will have a large power (99%) for investigating Hypothesis #5 using Bonferroni corrections. In general, our sample sizes will be able to detect effect sizes of at least 0.7 in absolute value with at least 90% power.

Hypothesis #6. The change in lactate/ATP ratio from baseline to 12 weeks will be computed for each patient. A one-tailed independent samples t-test will examine the null hypothesis of no differences in mean changes

between ubiquinol and placebo groups against the alternative that the mean change in patients on ubiquinol will be numerically smaller, which includes the possibility of a negative change. Similar tests will compare D-ribose versus placebo, the combination of ubiquinol + D-ribose versus placebo, and ubiquinol versus ubiquinol + D-ribose. Our sample sizes will give us a power of at least 90% to detect effect sizes of at least 0.7 in absolute value by using a 0.05 significance level and Bonferroni correction for the four comparisons.

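### Holm's procedure in place of plain Bonferroni over the four arm comparisons keeps the same 5% familywise limit and adds a little power: about 1 to 2 points at the design effect, 3 to 6 at 0.7

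*Combined protocol and SAP*

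**What the plan says.** C.5, Hypotheses #1 and #2, compares the change in KCCQ Clinical Summary score from baseline to week 12. For ubiquinol against placebo: "A two-tailed independent samples t-test will test the null hypothesis of no difference in mean change". The other three contrasts follow: "Similar tests will be used to compare D-ribose with placebo, ubiquinol + D-ribose with placebo, and ubiquinol versus ubiquinol + D-ribose". That makes a family of four.

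The planning values are also given there. The clinical target is that "an increase of at least 10 points with use of ubiquinol will be clinically important". On variability: "The combined estimated standard deviation for the increase was 12.3 points". Then: "This implies that Cohen effect sizes of at least 0.81". With 62 patients per group the plan states at least 98% power, "with Bonferroni correction for four comparisons" inside a nominal 0.05. The same rule applies to the Vigor score.

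Hypotheses #3 to #6 use the same family of four with the same correction. For the 6-minute walk test, for example, power of at least 90% at an effect size of 0.7 is stated "at a nominal 0.05 level of significance with Bonferroni correction for four comparisons". Hypothesis #6 differs only in using one-tailed tests. No step-down procedure is mentioned, and C.5 states no power for an effect smaller than 0.7.

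**The concern.** Under plain Bonferroni a comparison with p = 0.02 fails even when the other three are overwhelmingly significant. Holm orders the p-values and compares them in turn with 0.05/4, 0.05/3, 0.05/2 and 0.05, stopping at the first failure. It starts at the Bonferroni threshold and then relaxes, so it can never reject less. It protects the familywise error at 5% for any dependence between the tests, which matters here because the four contrasts share arms.

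The gain is largest when several comparisons are truly non-null together. The sponsor hopes for that pattern: C.5 says pilot results suggest that ubiquinol, and probably D-ribose, will each reach the 10-point target, and it plans to look for synergy. At stake is some avoidable loss of power, chiefly for the single-supplement comparisons and for ubiquinol against the combination.

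**Working it through.** **Inputs from C.5.** Familywise alpha 0.05; four comparisons; two-tailed t-tests on change; target 10 points; SD 12.3; 62 evaluable per arm, equal allocation; smallest effect with a power statement 0.7.

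**Assumptions added.** Normal data, equal SDs, and illustrative patterns of effects across arms, because the documents do not specify one. U is ubiquinol, D is D-ribose, P is placebo.

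**1. The plan's own figures.**
- Per-comparison alpha = 0.05/4 = 0.0125.
- d = 10/12.3 = 0.813. Noncentrality = d × √(62/2) = 0.813 × 5.568 = 4.53. The two-sided critical value at 0.0125 on 122 df is 2.535.
- Power from the noncentral t is 97.6% (97.5% with d rounded to 0.81); the normal approximation gives 97.9%. The stated 98% reproduces.
- At d = 0.7 power is 91.1%, against the stated 90% or more.
- Attrition: 62/0.9 = 68.9, so 69 per group.

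**2. The most Holm can add to one comparison.** Holm never tests a comparison more leniently than at 0.05, so its gain cannot exceed power at 0.05 minus power at 0.0125.
- d = 0.81: 99.4% − 97.5% = 1.9 points.
- d = 0.7: 97.2% − 91.1% = 6.0 points (unrounded 97.17 − 91.14).

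**3. The actual gain.** The four correlated t-tests were simulated with 62 per arm, 200,000 to 400,000 trials per pattern. Equal means all three active arms share the same effect; additive means the combination has twice the single effect.

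| Pattern | Comparison(s) | Bonferroni | Holm | Gain (points) |
|---|---|---|---|---|
| 0.81, equal | each active arm vs P | 97.5% | 98.6% | 1.1 |
| 0.81, additive | U vs P, D vs P, U vs U+D | 97.5% | 99.3–99.4% | 1.8–1.9 |
| 0.7, equal | each active arm vs P | 91.1% | 94.0% | 2.8 |
| 0.7, additive | U vs P, D vs P, U vs U+D | 91.1% | 96.6–97.1% | 5.4–5.9 |
| 0.5, additive (assumed) | U vs P | 59.9% | 73.4% | 13.5 |
| | D vs P | 59.9% | 72.2% | 12.3 |
| | U vs U+D | 59.8% | 74.4% | 14.6 |
| 0.4, additive (assumed) | U vs P, D vs P, U vs U+D | 38% | 48–50% | 10–11 |

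In the additive rows the combination against placebo gains almost nothing, because its power is already about 97% or higher.

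**4. Power to win at least one comparison.** Holm's first step is the Bonferroni test of the smallest p-value, so this power is identical under both methods (99.9% in the 0.5 additive pattern).

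**5. Familywise error.**
- No effect in any arm: 4.3% for both methods.
- All three placebo comparisons real at 0.81 and ubiquinol equal to the combination: about 1.3% for Bonferroni and 4.8% for Holm.

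Both stay within 5%. Holm gains its power by using more of the permitted error.

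**The case against.** The strongest reply is that nothing here is broken. Bonferroni is prespecified, valid and already counted in the sample size, and its stated power reproduces. At the plan's own design effect Holm can add at most 1.9 points. All of that stands.

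A reader who looks only at the 0.5 row might infer that Bonferroni costs this trial some 14 points of power. The documents do not support that. They give neither an effect near 0.5 nor an additive pattern as a design value, and with SD 12.3 an effect of 0.5 is 0.5 × 12.3 ≈ 6 points, below the plan's 10-point threshold. Nor is 14 an upper bound: other assumed patterns reach about 21 points for one comparison with d near 0.4.

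There is a partial answer on plausibility. The SD of 12.3 rests on ten pilot patients. Table 1 reproduces it as the total SD of both groups: √{[4(7.0² + 13.2²) + 2 × 5 × 6.85²]/9} = √(1362/9) = 12.3, where 6.85 is half the 13.7-point difference in means. Assuming normal data, the upper 95% limit is √(1362/2.70) = 22.5, at which 10 points is d = 10/22.5 ≈ 0.44. So effects of 0.4 to 0.5 cannot be dismissed, but they remain an assumption.

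It is also fair to say that Holm is not wholly without cost. Bonferroni tests have matching simultaneous intervals, and Holm's are less direct.

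**Conclusion.** The point holds as an optional efficiency gain. Holm keeps the same 5% familywise limit over the same four comparisons and is never less powerful. The gain per comparison is about 1 to 2 points at 0.81 and 3 to 6 points at 0.7. It is about 10 to 15 points only for assumed additive effects of 0.4 to 0.5 per supplement. The direction needs no assumption; the sizes rest on 62 evaluable patients per arm, normal data, equal SDs and the patterns shown.

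Two further inferences should be avoided. The equal 4.3% error rates do not mean that the two methods always have the same actual error; they share the limit, and the equality belongs to the case of no effect anywhere. And Holm within an outcome does nothing about multiplicity across outcomes: the correction in C.5 covers four comparisons per outcome, and this change leaves that scope as it is.

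**What to change.** Before unblinding, replace the Bonferroni correction with the Holm procedure wherever it appears in C.5 (Hypotheses #1 to #6), applied to the same four comparisons within each outcome at a familywise 0.05. Report Holm-adjusted p-values. Leave the sample size at 69 per group. Keep the power figures and label them as calculated under Bonferroni, since power under Holm is never lower.

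The cost is a short change of wording and one reporting decision. Bonferroni simultaneous intervals (98.75% each, from 1 − 0.05/4) can still be shown, with a note that one may occasionally include zero beside a Holm rejection.

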
A capillary finger stick blood sample (1.0 ml) will be obtained after subjects have completed the questionnaires and echocardiograms. Lactate concentration will be measured with a portable i-STAT handheld instrument using a CG4+ cartridge that requires 0.5 ml blood and takes 2 minutes to complete. Quality control tests will be performed on the i-STAT instrument each time prior to sampling. The lactate cartridge initiates a series of preset quality control diagnostics, from monitoring the quality of the sample to validating the reagent. The lactate cartridge contains sensitive biosensors on a silicon chip that is configured to perform that specific test. We will use 0.5 ml of venous blood for the ATP measurements and place it in 10 ml of distilled water. Using a probe called the AquaSnap Total system, ATP in solution will be measured. The specifically designed tip will collect 100 µl of solution, and then we will place the probe into the EnSURE™ instrument (ATP Test System). The EnSURE™ quality monitoring system detects real-time ATP down to 0.1 fmol within 15 seconds.

C.4. Preliminary Data. [name], our senior cardiologist, has more than 10 years of clinical experience in prescribing CoQ10, and for the past 4 years has prescribed the combination of ubiquinol (600 mg/day) and D-ribose (15 g/day) for patients with HFpEF. He has observed significant improvement in the health status of these patients using this combination of supplements. All subjects in our preliminary study reported that they complied with these doses by taking all daily required supplements in the morning with breakfast (compliance). Each subject tolerated these doses without any reported side effects (tolerance).

Table 1 summarizes the results of this preliminary study. Patients with HFpEF were given the KCCQ and the POMS Vigor subscale before and after 12 weeks of taking ubiquinol or ubiquinol plus D-ribose. We observed significant improvements (paired samples t-tests, $p < 0.05$) in the KCCQ clinical summary, functional status, self-efficacy, social interactions, quality of life, symptoms, and physical limitation scores as well as significant improvements in POMS Vigor scores. The increase in self-efficacy and social interactions was not a direct change but may have resulted from the improved level of vigor and reduced signs and symptoms of HF.

| Table 1 Variables | Ubiquinol Only (N = 5) | | Ubiquinol + D-ribose (N = 5) | |

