Analogous two-tailed independent samples t-tests will be used to compare changes in POMS scores. According to a linear regression of changes in POMS Vigor scores versus changes in the KCCQ Clinical Summary scores using our pilot data, a 10-point increase in KCCQ Clinical Summary scores predicted about a 6.5 point increase in Vigor scores. Thus, we believe that a 6.5-point increase in vigor in our subjects will be of clinical importance. Our pilot study also yielded an estimated standard deviation of 3.6 for 12 week changes in Vigor score, which implies that Cohen effect sizes of at least 1.8 are clinically important. Our sample sizes will provide 99% power to detect this or larger effect sizes at a nominal 0.05 significance level with Bonferroni correction for four comparisons. If assumptions of the t-test are not satisfied, transformations or the Mann-Whitney test will be applied. The five subjects of our pilot study who received ubiquinol showed a significant increase of 16.3 points in KCCQ Clinical Summary scores with respect to baseline ($t=5.23$, $df=4$, two-tailed paired samples $p=0.0064$). Similarly, the other five subjects of our pilot study who received ubiquinol + D-ribose showed a significant increase of 30 points with respect to baseline ($t=5.10$, $df=4$, two-tailed paired samples $p=0.007$). The 13.7-point increase produced by the independent effect of D-ribose was borderline significant ($t=2.06$, $df=9$, two-tailed independent samples $p=0.08$). These results from our small pilot study suggest a high likelihood that ubiquinol, and probably D-ribose, will produce clinically important increases of 10 points in KCCQ scores, which gives additional confidence in the success of our proposed study and in the potential clinical applications of ubiquinol.

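### The 6.5-point Vigor target (d = 1.8, 99% power) is not the Vigor counterpart of a 10-point KCCQ difference and is unsupported as a between-arm difference; the pilot data cap that counterpart at about 2.5 points

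*Combined protocol and SAP*

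**What the plan says.** Section C.5 (Hypotheses #1 and #2) plans two-sided t-tests on 12-week change for four pairs of arms: each active arm against placebo, and ubiquinol against ubiquinol + D-ribose. The Bonferroni correction gives 0.05/4 = 0.0125 per test, with 62 analysed per arm.

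- **KCCQ.** The target is 10 points. "The combined estimated standard deviation for the increase was 12.3 points", and the plan concludes: "This implies that Cohen effect sizes of at least 0.81" (10/12.3) are clinically important, with at least 98% power.
- **Vigor.** "Analogous two-tailed independent samples t-tests will be used to compare changes in POMS scores". The target comes from regressing Vigor change on KCCQ change in the pilot: "a 10-point increase in KCCQ Clinical Summary scores predicted about a 6.5 point increase in Vigor scores". From this the plan says "we believe that a 6.5-point increase in vigor in our subjects will be of clinical importance". For the spread it uses "an estimated standard deviation of 3.6 for 12 week changes in Vigor score". It sets 6.5 against that SD, "which implies that Cohen effect sizes of at least 1.8 are clinically important", and claims 99% power.

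The regression's slope, intercept and correlation are not reported. On the pilot itself, section C.4 says: "Patients with HFpEF were given the KCCQ and the POMS Vigor subscale before and after 12 weeks of taking ubiquinol or ubiquinol plus D-ribose". Table 1 has five patients on each regimen and no placebo group for these two measures.

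**The concern.** The plan treats 10 KCCQ points as 0.81 SD and then presents the Vigor change tied to those same 10 points as 1.8 SD. A least-squares line cannot do this: it turns a difference of 0.81 SD in the predictor into r × 0.81 SD in the outcome, and r cannot exceed 1. The 6.5 therefore looks like a predicted within-patient change, intercept included, and not the Vigor difference that goes with a KCCQ difference. A t-test between arms removes any change the arms share, so the two are interchangeable only under an assumption about placebo.

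At stake is how a Vigor result is read. This is the only power statement written specifically for Vigor, and it also names the clinically important size. Against a threshold of 6.5, a true difference of 2.5 points would look unimportant. A null result could also be taken as excluding, with 99% power, any Vigor effect that matches a 10-point KCCQ effect.

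**Working it through.** **Inputs.** Table 1, 12-week changes, n = 5 per group: KCCQ Clinical Summary +16.3 (SD 7.0) on ubiquinol and +30.0 (SD 13.2) on ubiquinol + D-ribose; Vigor +7.6 (SD 4.2) and +9.6 (SD 3.0). Section C.5: 62 per arm, two-sided alpha 0.0125, Vigor SD 3.6.

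**1. The plan's own figures.**
- Combined means: KCCQ 23.15, Vigor 8.6.
- KCCQ sum of squares: 4(7.0²) + 4(13.2²) + 10(6.85²) = 1362.2, so SD = √(1362.2/9) = 12.30.
- Vigor sum of squares: 4(4.2²) + 4(3.0²) + 10(1.0²) = 116.56, so SD = √(116.56/9) = 3.60.
- Both stated SDs are reproduced, so they come from these ten treated patients.
- Power by noncentral t (df 122, noncentrality d√(62/2)): d = 10/12.3 = 0.81 gives 97.6% (97.9% by normal approximation; stated 98%). d = 6.5/3.6 = 1.8 gives over 99.99% (stated 99%). Both hold.

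**2. Can 6.5 be a slope effect?** The slope is r × SD(Vigor)/SD(KCCQ). A slope of 0.65 needs r = 0.65 × 12.3/3.6 = 2.22, which is impossible.

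**3. Largest slope that Table 1 allows.** The cross-product is greatest when the two changes are perfectly correlated within each group:
- within groups: 4(7.0)(4.2) + 4(13.2)(3.0) = 276.0
- between groups: 10(6.85)(1.0) = 68.5
- total: 344.5

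Maximum slope = 344.5/1362.2 = 0.253, or 2.53 Vigor points per 10 KCCQ points. This has r = 344.5/√(1362.2 × 116.56) = 0.86 and d = 2.53/3.6 = 0.70.

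Forced through zero, the maximum is (10 × 23.15 × 8.6 + 344.5)/(1362.2 + 10 × 23.15²) = 2335.4/6721.4 = 0.347, or 3.5 points. A common within-group slope gives at most 276/892.96 = 0.309, or 3.1 points. The ubiquinol group alone gives at most 4.2/7.0 = 0.60, or 6.0 points. None reaches 6.5.

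**4. What 6.5 most plausibly is.** As a fitted value at a KCCQ change of 10 it is attainable. The line through (23.15, 8.6) and (10, 6.5) has slope 2.1/13.15 = 0.160, intercept 8.6 − 0.160 × 23.15 = 4.9, and r = 0.55. On that line 10 KCCQ points carry 1.6 Vigor points (95% CI about −0.4 to 3.6, df 8). This is a reconstruction from unreported coefficients and is illustrative only.

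**5. What 62 per arm can detect** (SD 3.6, two-sided alpha 0.0125, noncentral t):

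| Vigor difference | d | Power |
|---|---|---|
| 2.48 | 0.69 | 90% |
| 2.53 (ceiling in step 3) | 0.70 | 91% |
| 3.16 | 0.88 | 99% |
| 6.5 | 1.8 | >99.99% |

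**6. Dependence on placebo.** With a treated change of 6.5, power stays at 99% or more up to a placebo change of 6.5 − 3.16 = 3.3 points, and at 90% or more up to 6.5 − 2.48 = 4.0.

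**7. Ubiquinol against ubiquinol + D-ribose.** The pilot Vigor difference was 9.6 − 7.6 = 2.0, with SE √(4.2²/5 + 3.0²/5) = 2.31 and 95% CI −3.3 to 7.3. The interval includes 6.5, so it shows only how little the pilot says about this comparison.

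**The case against.** - **The design is unharmed.** This stands. Detecting d = 1.8 with 99% power needs only about 16 per arm, so Vigor did not set the 62. Power is about 91% at the 2.5-point ceiling.
- **The plan already covers the point.** Under Hypothesis #5 it says that d of 0.7 is in general detectable with at least 90% power, and 0.7 × 3.6 = 2.5. This stands as a source for the replacement figure, but it does not withdraw the Vigor-specific 1.8.
- **The fitted-value reading is inferred.** This stands in part. If KCCQ had been regressed on Vigor and the line inverted, 2.93/r would equal 6.5 at r = 0.45. The plan describes the opposite direction, and even then 6.5 would not be the Vigor change predicted from KCCQ.
- **The KCCQ target is also a within-patient change used between arms.** That is a fair parallel. The KCCQ threshold at least has outside prognostic support; the Vigor figure rests on the regression alone.
- **Any conversion from KCCQ to Vigor is an assumption.** This stands. A slope from ten treated patients need not carry a between-arm difference, so neither 1.6 nor 2.5 points is an established counterpart of 10 KCCQ points.

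A reader might infer that the Vigor comparison is underpowered, since power at 1.6 points is 48%. The documents do not support this: 1.6 is reconstructed, its interval spans zero and extends past the detectable 2.5, and no document makes it the true effect.

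**Conclusion.** The target is wrong as written, and the matter is minor. In the regression the plan describes, 6.5 Vigor points cannot be what a 10-point KCCQ difference carries. The ceiling is about 2.5 points (d 0.70) with an intercept, or about 3.5 through zero, against the stated 6.5 (d 1.8). As a between-arm difference, 6.5 needs an unstated and untested assumption of no Vigor change on placebo. That assumption does not help with ubiquinol against ubiquinol + D-ribose, where both arms are treated.

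The ceilings rest on Table 1 as printed and on an ordinary least-squares fit to those ten patients. The intercept of about 4.9 rests further on reading 6.5 as a fitted value. Two stronger conclusions do not follow: the 99% is not a miscalculation, and the sample size is not too small.

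**What to change.** In section C.5 (Hypotheses #1 and #2), remove 6.5 points, d = 1.8 and 99% as the between-arm target for Vigor. State instead that 62 per arm, at two-sided alpha 0.0125 and SD 3.6, gives 90% power for a Vigor difference of about 2.5 points (d about 0.69) in each of the four comparisons, in line with the general statement under Hypothesis #5. Present this as the detectable difference. If it is also to be called clinically important, that needs its own justification.

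If the pilot regression is kept, report its slope and intercept with confidence intervals and state the assumed placebo change.

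The cost is two or three rewritten sentences and a less favourable stated target. Sample size, tests and alpha are unchanged.
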